PPS	Per-protocol set
PSG	Polysomnography
PT	Preferred term
REM	Rapid eye movement
SAE	Serious adverse event
SAP	Statistical analysis plan
SCR set	Screened analysis set
SD	Standard deviation
SDS [©]	Sheehan Disability Scale [©]
SI	Standard international
sLSO	Subjective Latency to Sleep Onset
SOC	System organ class
SS	Safety set
sTST	Subjective Total Sleep Time
sWASO	Subjective Wake After Sleep Onset
SWS	Slow wave sleep
TBIL	Total bilirubin
TEAE	Treatment-emergent adverse event
TST	Total Sleep Time
TWS	Treatment withdrawal set
ULN	Upper limit of normal
VAS	Visual analog scale(s)
WASO	Wake After Sleep Onset
WHO	World Health Organization

1 INTRODUCTION

This statistical analysis plan (SAP) describes in detail the analyses and data presentation for the clinical study report (CSR) prepared for ID-078A301.

Obvious corrections to address minor formatting errors or spelling mistakes may be performed at the time of analysis without amending this and related documentation (e.g., mock shells).

Data will be analyzed by Idorsia and/or designated contract research organizations supervised by Idorsia using SAS[®] version 9.4 or higher and R version 3.4.3 or higher.

The analyses for the Independent Data Monitoring Committee (IDMC) closed session meetings will be performed by an Independent Statistical Analysis Center (ISAC) and are detailed in a separate SAP.

Protocol ID-078A301, Final Version 4, dated 30 July 2018 was used when writing this SAP.

A sub-study will be performed to collect data on subject preferences, which aims to enroll at least 360 subjects from the USA and Germany who are part of the approximately 900 subjects enrolled in the ID-078A301. The statistical analyses of the sub-study will be detailed in a separate document and reported separately.

Unless noted otherwise, summaries will be produced by treatment group [see Section 10.2].

2 STUDY DESIGN AND FLOW

This is a 3-month, multi-center, double-blind, randomized, placebo-controlled, parallel-group, Phase 3 study to assess the efficacy and safety of two doses (25 mg and 50 mg) of ACT-541468 in subjects with insomnia disorder.

[figure not shown]
Approximately 900 subjects per study will be randomized to either 25 mg ACT-541468, 50 mg ACT-541468 or placebo, in a 1:1:1 ratio.

Treatment allocation is further stratified by age into two categories: < 65 and ≥ 65 years. Approximately 40% of subjects will be elderly subjects (≥ 65 years old), of which approximately 5% will be above 75 years old.

The study will be conducted at approximately 75 sites in 10 countries.

The study design is shown in [Figure 1](#).

Figure 1 Study design for ID-078A301

The study comprises the following 3 phases: the screening phase, the treatment phase and the safety follow-up phase.

The **screening phase** starts with the signing of the informed consent form at Visit 1 and ends at Randomization at Visit 4. It includes the *Screening period* (from Visit 1 to Visit 2) and the *Run-in period* (from Visit 2 to Visit 4).

The **double-blind (DB) treatment phase** starts with the first dose of DB study treatment in the first evening of the randomization visit (Visit 4) and lasts until the second morning of Visit 8 after all second morning assessments have been performed, i.e., End-of-Double-Blind-Treatment (EODBT).

The **safety follow-up phase** starts from EODBT and lasts until End-of-Study (EOS). It consists of a single-blind placebo *Run-out period* (from the evening of Visit 9 until after all visit assessments have been performed at Visit 10, i.e., End-of-Treatment [EOT]) and a *Safety follow-up period* (from EOT until EOS).

See Section 12.2 for detailed definitions of the study periods.

Subjects who do not prematurely discontinue DB study treatment and who complete the Run-out period will be eligible to enter the ID-078A303 extension study. The statistical analyses for ID-078A303 CSR will be detailed in a separate document and reported separately.

3 OBJECTIVES

The main objectives of the study are to assess efficacy and safety of ACT-541468 in subjects with insomnia disorder.

Efficacy will be evaluated primarily by the drug effects on sleep onset and sleep maintenance.

3.1 Primary objectives

To evaluate the efficacy of 25 mg and 50 mg ACT-541468 on objective sleep parameters in subjects with insomnia disorder.

3.2 Secondary objectives

To evaluate the efficacy of 25 mg and 50 mg ACT-541468 on subjective sleep parameters and next-day functioning in subjects with insomnia disorder.

3.3 Safety objectives

To assess the safety and tolerability of ACT-541468 in subjects with insomnia disorder during treatment and upon treatment discontinuation.

4 ANALYSIS SETS

4.1 Definitions of analysis sets

A subject must have given informed consent before being included in any analysis set.

The number of subjects in each analysis set defined below will be tabulated. Any subject excluded along with reason(s) for exclusion from Per-protocol set (PPS), Treatment withdrawal set (TWS), or Pharmacokinetic (PK) analysis set will be summarized and listed.

4.1.1 Screened analysis set

The Screened analysis set (SCR set) comprises all subjects who entered screening and have a subject identification number.

Summaries based on the SCR set will be presented as one group (i.e., all subjects), unless specified otherwise. For summaries by treatment group, subjects will be evaluated according to the treatment they have been assigned to.

4.1.2 Full analysis set

The Full analysis set (FAS) comprises all subjects assigned (i.e., randomized) to a DB study treatment.

In order to adhere to the intention-to-treat principle as much as possible:

- Subjects will be evaluated according to the treatment and strata they have been assigned to, which may differ from the treatment they received.
- All available data will be included.

4.1.3 Per-protocol set

The PPS comprises all subjects from the FAS who received at least one dose of DB study treatment and who complied with the protocol sufficiently to be likely to exhibit the treatment effects.

Criteria for sufficient compliance:

- Absence of major protocol deviations (i.e., those leading to exclusion from the PPS), as defined in a separate protocol deviation (PD) document that will be finalized before unblinding treatment codes.
- DB study treatment compliance is $\geq 70\%$ (as calculated in Section 5.4.2).

Subjects not meeting the criteria for sufficient compliance will be excluded from the PPS. Subjects will be evaluated according to the treatment they have been assigned and actual stratum they belong to.

4.1.4 Safety set

The Safety set (SS) comprises all subjects who received at least one dose of DB study treatment.

Subjects will be evaluated according to the actual treatment they received, which may differ from the randomly assigned treatment.

Actual treatment received is defined as:

- the assigned DB study treatment when received at least once,
- the first DB study treatment received if the assigned DB study treatment was never received.

4.1.5 Treatment withdrawal set

The TWS comprises all subjects included in the SS who received at least one dose of single-blind placebo treatment in the Run-out period.

Subjects will be evaluated according to the actual treatment they received, which may differ from the randomly assigned treatment.

4.1.6 Pharmacokinetic analysis set

The PK set comprises all subjects in the SS who have at least one PK sample collected after initiation of DB study treatment.

Subjects will be evaluated according to the actual treatment they received. Subjects receiving placebo will be excluded from the PK set.

4.2 Usage of the analysis sets

The analyses of efficacy endpoints as well as demographic and baseline disease characteristics will be performed using the FAS, and the PPS for certain sensitivity analyses.

The SS will be used for the analysis of safety endpoints (including previous and concomitant medications, and study treatment exposure).

The TWS will be used for the analysis of endpoints used to assess withdrawal symptoms (e.g., Benzodiazepine Withdrawal Symptom Questionnaire [BWSQ] Total score) and rebound insomnia (i.e., objective sleep parameters Wake After Sleep Onset [WASO], Latency to Persistent Sleep [LPS] and subjective TST [sTST]).

The PK set will be used for the analysis of ACT-541468 plasma concentrations 9–10 h post-dose.

5 STUDY SUBJECTS' VARIABLES AND ANALYSES

5.1 Subject disposition

5.1.1 Screening failures

Screening failures will be summarized based on the SCR set and will include:

- Number (%) of subjects who discontinued during the screening phase (based on 'Was the subject randomized?' recorded as 'No' in the 'Randomization' page); this summary will be broken down as follows:
 - Number (%) of subjects who discontinued during the Screening period (based on 'Was the subject randomized?' recorded as 'No' in the 'Randomization' page, and missing 'Treatment start date' in the 'Study Single-Blind [Run-In] Treatment Log' page).
 - Number (%) of subjects who discontinued during the Run-in period (based on 'Was the subject randomized?' recorded as 'No' in the 'Randomization' page, and a non-missing 'Treatment start date' in the 'Study Single-Blind [Run-In] Treatment Log' page).
- Primary reason for screening phase discontinuation (based on reason for not randomized entered on the 'Randomization' page); this summary will be broken down as follows:
 - Primary reason for Screening period discontinuation (based on reason for not randomized entered on the 'Randomization' page for subjects missing 'Treatment start date' in the 'Study Single-Blind [Run-In] Treatment Log' page).
 - Primary reason for Run-in period discontinuation (based on reason for not randomized entered on the 'Randomization' page for subjects with a non-missing 'Treatment start date' in the 'Study Single-Blind [Run-In] Treatment Log' page).

- Primary reason for premature single-blind placebo treatment discontinuation in the run-in period (based on reason for treatment discontinuation entered on the ‘Study Single-Blind [Run-In] Treatment Log’ page).

All reasons for screening failure will be listed using the SCR set.

Of note, subjects are not permitted to be re-screened.

5.1.2 Study disposition

Study disposition will be summarized based on the SCR set, presented by randomized treatment group and all screened subjects combined, and will include:

- Number of subjects screened.
- Number (%) of subjects treated in the single-blind placebo treatment run-in period (based on a non-missing ‘Treatment start date’ in the ‘Study Single-Blind [Run-In] Treatment Log’ page).
- Number (%) of subjects who completed single-blind placebo treatment run-in period (based on ‘Reason for treatment stop’ entered as ‘Completion as per protocol’ in the ‘Study Single-Blind [Run-In] Treatment Log’ page).
- Number (%) of subjects randomized (based on non-missing randomization number).
- Number (%) of subjects treated in the DB study period (based on non-missing ‘Treatment start date’ in the ‘Study Double Blind Treatment Log’ page).
- Number (%) of subjects who completed the DB study period (based on ‘Reason for treatment stop’ entered as ‘Completion as per protocol’ in the ‘Study Double Blind Treatment Log’ page).
- Number (%) of subjects treated in the single-blind placebo treatment Run-out period (based on a non-missing ‘Treatment start date’ in the ‘Study Single-Blind [Run-Out] Treatment Log’ page).
- Number (%) of subjects who completed single-blind placebo treatment Run-out period (based on ‘Reason for treatment stop’ entered as ‘Completion as per protocol’ in the ‘Study Single-Blind [Run-Out] Treatment Log’ page).
- Number (%) of subjects completing the study (based on ‘Did the subject complete the study?’ recorded as ‘Yes’ in the ‘End of Study Status’ page).
- Number (%) of subjects completing the study and not entering the extension study (based on ‘Did the subject complete the study?’ recorded as ‘Yes’ in the ‘End of Study Status’ page, and ‘Did the subject sign the informed consent to participate in the extension study?’ recorded as ‘No’ in the ‘Study Extension’ page).
- Number (%) of subjects entering the extension study (based on ‘Did the subject sign the informed consent to participate in the extension study?’ recorded as ‘Yes’ in the ‘Study Extension’ page).

5.1.3 Study and study treatment completion/discontinuation

The following summary will be based on the FAS and presented by treatment group and all treatment groups combined:

- Number (%) of subjects who prematurely discontinued DB study treatment (based on reason for treatment stop entered as 'Discontinuation' in the 'Study Double Blind Treatment Log' page).
- Primary reason for premature DB study treatment discontinuation (based on reason for treatment discontinuation entered on the 'Study Double Blind Treatment Log' page).

All reasons for premature DB study treatment discontinuation will be listed based on the FAS.

The following summary will be based on the FAS and presented by treatment group and all treatment groups combined:

- Number (%) of subjects who prematurely discontinued from the study (based on non-missing reason for stopping study entered in the 'End of Study Status' page).
- Primary reason for premature discontinuation from the study (based on reason for stopping study entered in the 'End of Study Status' page).

All reasons for premature study discontinuation will be listed based on the FAS.

The following summary will be based on the TWS and presented by treatment group and all treatment groups combined:

- Number (%) of subjects who prematurely discontinued single-blind placebo treatment in the Run-out period (based on reason for treatment stop entered as 'Discontinuation' in the 'Study Single-Blind [Run-Out] Treatment Log' page).
- Primary reason for premature single-blind placebo treatment discontinuation in the Run-out period (based on reason for treatment discontinuation entered on the 'Study Single-Blind [Run-Out] Treatment Log' page).

All reasons for premature single-blind placebo treatment discontinuation in the Run-out period will be listed based on the TWS.

5.1.4 Study enrollment

The number (%) of subjects randomized will be displayed by country and site based on the FAS by treatment group and all treatment groups combined.

The randomization scheme and codes will be listed for randomized subjects only.

5.2 Protocol deviations

The FAS will be used for the summary of PDs. All PDs and Important PDs will be summarized in separate tables as per pre-specified category (i.e., selection criteria, Investigational Medicinal Product, study conduct/procedure, forbidden medication, withdrawal criteria and other) by treatment group and all treatment groups combined.

A subject with multiple occurrences of a protocol deviation is counted only once per protocol deviation category.

A listing of protocol deviations will be provided using the FAS.

5.3 Subject characteristics

Unless noted otherwise, summaries and listings described in this section will be based on the FAS.

Summaries will be produced by treatment group and all treatment groups combined. Data will be listed individually by subject.

5.3.1 Demographics and baseline characteristics

Demographic data at screening, including age, sex, race, ethnicity, height, weight, body mass index (BMI) and region (US, other), will be summarized and listed.

The number (%) of subjects randomized in each age category (< 18, 18 – < 65, 65 – < 75, 75 – < 85, 65 – < 85, ≥ 85 years at screening), in each BMI category (< 25, 25 – 30, > 30 kg/m² at screening), and in each region (US, other) will be further summarized.

The number of subjects treated in each age category (< 18, 18 – < 65, 65 – < 85 and ≥ 85 years at screening) by sex will be summarized based on the SS.

5.3.2 Baseline disease characteristics

Baseline disease characteristics include dissatisfaction with sleep quantity or quality (Y/N), difficulty initiating sleep (Y/N), difficulty maintaining sleep characterized by frequent awakenings or problems returning to sleep after awakenings (Y/N), early morning awakening with inability to return to sleep (Y/N) and sleep disturbance causing significant distress or impairment in social, occupational, educational, academic, behavioral, or other important areas of functioning (Y/N).

These baseline disease characteristics, including the time since insomnia diagnosis (in years) at randomization, will be listed and summarized.

An incomplete (day or month missing) or missing insomnia diagnosis date will be imputed using the 15th day of the month (if only the day is missing) or 1st of July (if day and month are missing).

If the insomnia diagnosis imputed date is after the randomization date, then the randomization date –1 day will be used as insomnia diagnosis date.

5.3.3 Previous and concomitant diseases at screening

Relevant medical history and current medical conditions will be coded using MedDRA terminology.

Any disease or diagnosis is defined as previous if ‘Ongoing at informed consent signed’ is answered as ‘No’; all other diseases/diagnoses are considered as study concomitant (where answer is ‘Yes’).

Medical history and current (ongoing) medical conditions, excluding insomnia-related conditions and symptoms, will be summarized separately and listed. Summaries will be presented for each treatment group by primary system organ class (SOC) and preferred term (PT). Medical history will be sorted by SOC and PT within each SOC by descending frequency based on all treatment groups combined.

The MedDRA version used for reporting will be specified in the footnote of the applicable output.

5.3.4 Previous and concomitant therapy

Therapies collected will be coded using the WHO Drug Global reference dictionary that employs the WHO Anatomical Therapeutic Chemical (ATC) classification system. The WHO Drug Global version used for reporting will be specified in the footnote of the applicable output.

Previous therapies are any treatments for which the end date is prior to signing of the informed consent form. A previous therapy is to be recorded in the ‘Previous/Concomitant Medication’ page if discontinued less than 30 days prior to signing of the informed consent form, however, all previous therapies recorded will be reported.

Study-concomitant therapies are any treatments that are either ongoing at the signing of informed consent, or initiated during the time from the signing of informed consent up to EOS. The use of all study-concomitant therapies (including contraceptives and traditional and alternative medicines, e.g., plant-, animal-, or mineral-based medicines) is to be recorded in the ‘Previous/Concomitant Medication’ page.

Double-blind study treatment concomitant therapies (a subset of study-concomitant therapies) are any treatments that are either ongoing at the start of DB study treatment or initiated during the DB study period until 1 day after the last dose of DB study treatment.

Number (%) of subjects having taken at least one previous or concomitant therapy will be summarized by ATC classification level 4 (or next highest available level) and individual preferred name within each ATC classification based on the SS. Previous and concomitant

therapy will be sorted by ATC class and preferred name within each ATC class by descending frequency based on all treatment groups combined.

Summary tables will be provided for previous, study-concomitant and DB study treatment-concomitant therapies separately. An additional summary table will be provided for DB study treatment concomitant therapies at Baseline (i.e., therapy started on, or is ongoing at, the DB study treatment start date). All concomitant therapies will be listed using the SS. The period (e.g., run-in, DB, run-out [Section 12.2]) for which the concomitant therapy started will be displayed in the listing and those related to an adverse event (AE) will be flagged.

The number (%) of subjects currently on cognitive behavioral therapies and reasons for not using cognitive behavioral therapy will be summarized and listed using both the FAS and the SCR set. Cognitive behavioral therapy is not coded.

An incomplete (day or month missing) or missing concomitant therapy date will be imputed as described in Table 1. The 'lower limit' and 'upper limit' refer to the earliest and latest possible dates, respectively. As an example: If concomitant therapy start date is MAR2017 (day missing), the lower limit is 01MAR2017 and the upper limit is 31MAR2017; If concomitant therapy start date is 2017 (day and month missing), the lower limit is 01JAN2017 and the upper limit is 31DEC2017.

Table 1 Imputation rules for an incomplete or missing concomitant therapy date

Field	Incomplete date	Missing date
Concomitant therapy end date	The upper limit.	No imputation; the therapy is considered as ongoing.
Concomitant therapy start date	
The rules below apply in the order presented:
 
 1. If the (imputed) concomitant therapy end date is on or after the start of DB study treatment, and if the DB study treatment start falls within the upper and lower limits (inclusive), the DB study treatment start date is used. 2. If the (imputed) concomitant therapy end date is on or after the start of run-in single-blind placebo treatment, and if the run-in single-blind placebo treatment start falls within the upper and lower limits (inclusive), the run-in single-blind placebo treatment start date is used. 3. If the concomitant therapy resolution date is missing, and: 
 a. if the DB study treatment start falls within the upper and lower limits (inclusive), the DB study treatment start date is used; else: 
 b. if the run-in single-blind placebo treatment start falls within the upper and lower limits (inclusive), the run-in single-blind placebo treatment start date is used. 4. In all the other cases, the lower limit is used. 	Whichever is the earlier of the concomitant therapy end date or DB study treatment start date.

DB = double-blind.

The purpose of imputing concomitant therapy dates is only to assign a concomitant therapy to a specific treatment phase for the summary tables. No imputed date is considered in the medical evaluation of a concomitant therapy causal relationship to an individual AE.

5.4 Study treatment exposure and compliance

Unless noted otherwise, summaries and listings described in this section will be based on the SS.

5.4.1 Exposure

The duration of single-blind placebo run-in treatment, DB study treatment, and single-blind placebo run-out treatment (including categories: ≤ 1 , $> 1 - 2$, $> 2 - 3$, $> 3 - 4$, $> 4 - 6$,

> 6 – 8, > 8 – 10, > 10 – 11, > 11 – 12, > 12 – 13, > 13 weeks for DB study treatment; 0, > 0 – 2, > 2 – 5, > 5 – 9, > 9 – 14, > 14 – 20, > 20 days for single-blind placebo run-in treatment; and 0, 1, 2, 3, 4, 5, 6, 7, 8, 9, ≥ 10 days for single-blind placebo run-out treatment) and duration in subject-years will be summarized. The definition of a year is 365.25 days.

The duration of treatment (in days) is defined as the difference between the respective (run-in/DB/run-out) treatment end date and the respective (run-in/DB/run-out) treatment start date plus one day. This calculation ignores periods of treatment interruption. The summary for run-out will be based on the TWS.

The duration of treatment along with reason for treatment stop will be listed.

5.4.2 Study treatment compliance

Study treatment compliance will be assessed through study treatment accountability.

Study treatment compliance per wallet dispensed is entered in the electronic case report form (eCRF) for the Run-in period, the DB study period, and the Run-out period and will only be listed.

The following formula will be used to calculate compliance for each of these periods:

Study treatment compliance (%) = $[(\text{number of tablets dispensed} - \text{number of tablets returned}^*) / (\text{treatment duration} - \text{total duration of treatment interruptions})] \times 100$

* If a subject did not return his wallet (e.g., it is lost), compliance will not be calculated and the compliance for the period will be set to missing.

Treatment duration and total duration of treatment interruptions in Run-in, DB, or Run-out periods are calculated using the dedicated eCRF page ‘Study Treatment Log’ as follows:

- Treatment duration (days) = date of last drug intake of DB study treatment (run-in / run-out single-blind placebo treatment) – date of first drug intake of DB study treatment (run-in / run-out single-blind placebo treatment) + 1 day.
- Total duration of treatment interruptions (days) is the sum of all the treatment interruptions’ durations. A treatment interruption duration = date restarted DB study treatment (run-in / run-out single-blind placebo treatment) – end date of DB study treatment (run-in / run-out single-blind placebo treatment) due to an interruption – 1 day. For example, if a subject stopped his/her treatment on 19MAR2019 and started again on 23MAR2019, as the treatment is taken on the start and end dates, the calculation will be 23MAR2019–19MAR2019 – 1 day = 3 days of interruption. Should the subject interrupt the treatment again for 7 days, the total duration of interruptions will be 10 days. For subjects who complete the study treatment for a given study period but end on an interruption before continuing study treatment in the next study period,

the start date of the next study period will be used as the date restarted study treatment of the given study period. E.g., if a subject completed DB study treatment with an interruption on 23JUN2019 and then started the treatment withdrawal period on 26JUN2019, the duration of that treatment interruption will be $(26\text{JUN}2019 - 23\text{JUN}2019) - 1 \text{ day} = 2 \text{ days}$.

The percentage of days treated is defined as follows:

- Percentage of days treated = $100 \times (\text{treatment duration} - \text{total duration of treatment interruptions}) / \text{treatment duration}$.

Study treatment compliance (including categories 0%, > 0% – < 50%, 50% – < 70%, 70% – < 80%, 80% – < 90%, 90% – < 100%, 100%, > 100%), number of treatment interruptions per subject by category (0, 1, 2, 3, 4, > 4 interruptions), duration of treatment interruptions and percentage of days treated (including categories 0%, > 0% – < 50%, 50% – < 70%, 70% – < 80%, 80% – < 90%, 90% – < 100%, 100%) will be summarized for Run-in, DB and Run-out periods, separately. The summaries of the Run-out period will be based on the TWS.

The number (%) of subjects who have treatment interruptions, and the corresponding reasons will be tabulated.

Study treatment compliance, dispensing and accountability data will be listed.

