12 GENERAL DEFINITIONS AND DERIVATIONS

12.1 Treatment start and end dates

Run-in single-blind placebo treatment start or end date is the earliest or latest, respectively, date of dose intake recorded on the 'Study Single-Blind (Run-In) Treatment Log' page.

DB study treatment start or end date is the earliest or latest, respectively, date of dose intake recorded on the 'Study Double Blind Treatment Log' page.

Run-out single-blind placebo treatment start and end date is the earliest and latest date of dose intake recorded on the 'Study Single-Blind (Run-Out) Treatment Log' page.

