12.2 Study periods

The Screening period is defined as the time from the informed consent date until one day before the Run-in period start date.

The Run-in period is defined as the time from the start of the run-in single-blind placebo treatment to one day before start of DB study treatment or, for those not starting DB study treatment, to run-in single-blind placebo treatment end date.

The DB study period is defined as the time from the day of DB study treatment start until the day of EODBT (Visit 8, 2nd morning), or, for those who prematurely discontinued DB study treatment (i.e., those without an EODBT date), until one day after DB study treatment end date (if the treatment is taken before midnight) or the day of DB study treatment end date (if the treatment is taken after midnight). Time of treatment intake between 00:00 and 11:59 is considered as 'after midnight', while a time between 12:00 and 23:59 is considered as 'before midnight'. For any missing or incomplete time, it is presumed that the treatment was taken before midnight. For subjects who complete DB study treatment with an

interruption before continuing the run-out single-blind placebo treatment, the end of DB study period is the run-out single-blind placebo treatment start date – 1 day.

For those subjects in the TWS, the treatment withdrawal period (or Run-out period) is defined as the time from one day after the end of the DB study period to the latter of seven days after the end of the DB study period or Visit 10 date.

The safety follow-up period is defined as the time from one day after the end of the treatment withdrawal period for those starting the treatment withdrawal period (i.e., subjects in the TWS) until EOS date; or from one day after the end of the DB study period for those not starting the treatment withdrawal period until EOS date.

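### SAP 5.4.2 subtracts end-of-period interruption days that its treatment duration never contained, so compliance is overstated for completers who end on an interruption, and the 70% per-protocol decision can change

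*SAP*

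**What the plan says.** SAP 4.1.3 admits a subject to the Per-Protocol Set (PPS) on three conditions: at least one double-blind (DB) dose, no major protocol deviation, and DB compliance of at least 70% by the 5.4.2 calculation. "Subjects not meeting the criteria for sufficient compliance will be excluded from the PPS". The major deviations are "as defined in a separate protocol deviation (PD) document that will be finalized before unblinding treatment codes"; that document was not available here.

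SAP 5.4.2 defines compliance as tablets dispensed minus tablets returned, divided by treatment duration minus total interruption days. Duration runs from first to last intake: "Treatment duration (days) = date of last drug intake of DB study treatment", less the date of first intake, plus one day. SAP 12.1 agrees: "DB study treatment start or end date is the earliest or latest, respectively, date of dose intake recorded". An interruption lasts from the stop date to the restart date, less one day, because 5.4.2 states that a dose is taken on both dates. For a subject who completes a period on an interruption, "the start date of the next study period will be used as the date restarted study treatment of the given study period".

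SAP 12.2 handles the same subjects in the period definition. If DB treatment is completed with an "interruption before continuing the run-out single-blind placebo treatment, the end of DB study period is the run-out single-blind placebo treatment start date", less one day.

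SAP 5.4.2 also tabulates "duration of treatment interruptions and percentage of days treated", using the same duration and the same interruption total.

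Protocol 5.1.7.2 uses another denominator: the days on which treatment was due according to actual visit dates. It sets a 70% expectation from Day 1 to end of double-blind treatment (EODBT) and treats lower values as a protocol deviation. Protocol 10.1.3 names exposure to treatment among the PPS criteria.

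**The concern.** For a completer who ends on an interruption, the two parts of the denominator cover different stretches of time. The duration stops at the last dose, but the interruption total includes days after it. Subtracting those days makes the denominator too small and the compliance figure too large.

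Two outputs are at stake. The 70% rule can keep in the PPS a subject who falls short by the SAP's own duration. The compliance table will also place fully adherent subjects in its above-100% category, together with subjects who used extra tablets. Percentage of days treated contains the same mismatch and goes wrong in the other direction.

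A secondary point concerns what the 70% rule can detect. Because the duration ends at the last dose and logged gaps are removed, early stopping and logged interruptions do not lower the figure. Protocol 5.1.9 encourages subjects who stop treatment to continue planned visits, so off-drug values could reach a set meant for subjects likely to show the treatment effect, unless another criterion removes them.

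**Working it through.** **Inputs.** The formulas and worked dates are from SAP 5.4.2, the end-date definition from SAP 12.1 and the period end from SAP 12.2. The planned DB length is 84 days, window 82 to 86 (protocol Table 1). Placing the SAP's example gap on particular study days is an assumption.

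**The SAP's own examples reproduce.** 19 to 23 March 2019: 23 − 19 − 1 = 3 days, and with a further 7-day gap the total is 10. Trailing example, 23 to 26 June 2019: 26 − 23 − 1 = 2 days, namely 24 and 25 June. Since a dose is taken on the stop date, the last DB intake is 23 June and the duration ends that day. Both subtracted days lie outside it.

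**SAP-length gap, last dose Day 82, run-out start Day 85.** Interruption = 85 − 82 − 1 = 2. Denominator = 82 − 2 = 80.

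| Tablets used | SAP 5.4.2 | Against the 82-day duration |
|---|---|---|
| 82 | 82/80 = 102.5% | 82/82 = 100% |
| 57 | 57/80 = 71.3%, passes | 57/82 = 69.5%, fails |
| 56 | 56/80 = 70.0%, passes | 56/82 = 68.3%, fails |

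Across the visit window, perfect intake reads 80/78 = 102.6% (82-day period) to 84/82 = 102.4% (86-day period).

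**Longer gap, last dose Day 70, run-out start Day 85.** Interruption = 85 − 70 − 1 = 14. Denominator = 70 − 14 = 56.
- Perfect intake: 70/56 = 125%.
- 40 tablets: 40/56 = 71.4%, a pass, against 40/70 = 57.1%.
- Percentage of days treated: (70 − 14)/70 = 80.0%, whereas 70 of 84 days, 83.3%, were dosed.

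For the 2-day gap, percentage of days treated is nearly right by coincidence: 80/82 = 97.56% against 82/84 = 97.62%.

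**Comparing two repairs on the Day 70 case.**
- Extend the duration to run-out start minus one day (84 days): compliance 70/(84 − 14) = 100%; days treated 70/84 = 83.3%.
- Keep 70 days and drop the subtraction: compliance 70/70 = 100%; days treated 70/70 = 100%, which hides the 14-day gap.

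**Secondary point.** Stopping after 1 or 10 tablets, all taken: 1/1 = 10/10 = 100%. A logged 26-day gap in an 84-day span: 58/(84 − 26) = 100%. The same 26 doses missed without a log entry: 58/84 = 69.0%, which fails.

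**Possible effect of early stoppers on the PPS estimate.** SAP 6.1.4 reports 14 stops among 356 Phase 2 subjects over 1 month. Leaving out 4 randomized in error or not meeting criteria and 2 withdrawals of consent gives 8/356 = 2.25%. Applied to the planned 15-minute difference: 15 × 0.0225 = 0.34 min. This pools all arms. At that rate 900 subjects give about 20 stops; if all were in one active arm, 20/300 = 6.7% and 15 × 0.067 = 1.0 min. Both calculations assume that stoppers attend the polysomnography visits and keep no drug effect. The unadjusted standard error is 40 × √(2/300) = 3.27 min.

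**The case against.** Four arguments can be made for leaving the text alone.

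First, the trailing case is rare and small. At the SAP's own gap length only two tablet counts change the decision. The Day 70 example needs a subject recorded as a completer who missed both Visit 8 laboratory-night doses, and the 40-tablet pass needs 30 further unlogged misses. This stands as a limit on size: the documents give no frequency, and the longer gaps are illustrations. It does not make the formula right.

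Second, compliance while on drug is a legitimate quantity, distinct from persistence, and the SAP tabulates duration, interruptions and discontinuations separately. This largely stands for early stopping and logged gaps. It does not cover the trailing subtraction, which is wrong under any definition of the denominator.

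Third, other safeguards exist. The protocol deviation document may exclude short exposure or long gaps, SAP 5.2 has deviation categories for investigational product and withdrawal criteria, and protocol 5.1.7.2 makes compliance below 70% by the protocol formula a deviation. A reader might infer from the 100% score after one tablet that early stoppers will enter the PPS. The documents do not support that, because the deviation document is unseen.

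Fourth, a reader might infer that the SAP contradicts the protocol. That is too strong. The 5.1.7.2 formula is for site staff to enter in the eCRF, and SAP 5.4.2 keeps the eCRF value as a listing. Protocol 10.1.3 sets neither a 70% rule nor a minimum exposure, and protocol section 10 leaves derivations to the SAP. The protocol denominator is also not fully specified for early stoppers: SAP 12.2 has a separate rule "for those who prematurely discontinued DB study treatment (i.e., those without an EODBT date"). What remains is a difference in denominator that neither SAP 13.1 nor 13.3 mentions.

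**Conclusion.** The trailing-interruption rule is wrong as written, on the SAP's own definitions and worked dates. It inflates compliance by about 2.5 percentage points for a fully adherent subject with a 2-day gap, and by more for longer gaps. It can move a subject from just below to just above the 70% threshold. The day counts assume a planned period of 84 days and the chosen position of the gap; the direction of the error depends on neither. The rule is worded for any study period, so run-in compliance has the same fault, but that figure does not feed the PPS.

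The blindness to early stopping and logged gaps is a point to confirm, not an established defect. The rule does detect missed doses that were not logged as interruptions.

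The effect on the PPS estimate is likely small. A reader might take 0.34 min as a ceiling, but it is not one: it applies a pooled 1-month rate to an active arm, and SAP 6.1.4 expects a slightly higher rate in Phase 3. No upper bound follows from the documents.

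Impact is confined to the supportive PPS analysis (SAP 6.1.8) and the compliance tables. The confirmatory tests use the Full Analysis Set and are unaffected. Severity: minor.

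**What to change.** Before unblinding:

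1. In SAP 5.4.2, for subjects who complete DB treatment on an interruption, define treatment duration as running to run-out start minus one day, as SAP 12.2 does for the DB period. Use it for both compliance and percentage of days treated. Do not simply drop the subtraction, for the reason shown in the comparison of repairs. Apply the matching rule to run-in, ending the day before DB start.
2. Confirm that the protocol deviation document covers exposure, including how a protocol 5.1.7.2 value below 70% is treated, and cross-refer to it in SAP 4.1.3. If it does not, add an exposure criterion there in line with protocol 10.1.3.
3. Note in SAP section 13 that the compliance denominator differs from that of protocol 5.1.7.2.

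The cost is a few lines of SAP text and one derived variable. If an exposure criterion has to be added, the PPS becomes slightly smaller and more selected on post-randomization discontinuation, which should be stated when it is interpreted.
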